10.7.3. Part 1 Analyses

Part 1 will be analyzed separately as an a priori powered study. A Statistical Analysis Plan will be developed that describes the analyses to address the study's primary, secondary, and exploratory objectives.

The following provides an outline of the methods for the main comparisons between randomized arms, particularly for the primary outcome measure.

Analyses involving randomized comparisons will include all randomized participants who received the first (confirmed) dose of study treatment, according to a modified intention-to-treat (m-ITT) approach. Participants who do not receive the first (confirmed) dose will be replaced. Unless stated otherwise, the date of randomization will be the time origin for analysis (Day 1). Additional per-protocol analyses may be performed, particularly for virology efficacy endpoints. Missing data are expected to be uncommon (<5 to 10% of participants). Losses to follow-up will be assumed non-informative and complete-case analyses will be conducted.

This is a virology proof-of-principle study, as such a type I error probability of 10% (α =0.10) will be used throughout, with no planned adjustments for multiplicity or primary or secondary endpoints. Throughout, all statistical tests will be two-sided and "exact" statistical procedures that do not rely on large sample assumptions will be applied where computationally feasible.

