3.2. Sample Size Considerations

3.2.1. Sample Size Determination

This study is designed to evaluate the antiviral activity of EIDD-2801 by estimating the time (days) until elimination of viral RNA in NP swabs in people who receive EIDD-2801 compared to those who receive a blinded placebo. Kaplan-Meier (KM) estimation will be used with a corresponding exact log-rank test (for Part 1). The median time (days) until first non-detectable SARS-Cov-2 NP swabs will be estimated in each trial arm. Anticipating up to 10% missing data, enrolling n=44 participants total (approximately 22 per arm) in Part 1 will provide 88% power to detect a risk difference (active – placebo) of -35% for the primary endpoint using an alpha=0.10 type I error rate and with viral RNA measured at Days 1, 3, 5, 7, 14, and 28.

For Parts 2 to 9, no formal statistical hypotheses will be tested. In consideration of analysis of secondary virology endpoints in these dose range finding cohorts, separate power calculations were done for Parts 2 to 9. For Parts 2 to 9, sample size sensitivity was estimated based on the combined study parts to compare the change from baseline in viral RNA between participants treated with EIDD-2801 versus participants treated with placebo. A total 96 participants in the

active group and 32 participants in the placebo group will achieve 83% power to detect a between group difference of at least 0.6 SD in SARS-CoV-2 viral RNA change from baseline with a type I error rate of alpha=0.05 using a two-sided test.

The proposed total sample size for the study is up to approximately 172 fully evaluable participants. If participants in a dose group drop out or otherwise have missing or unevaluable primary or key secondary virology endpoint data, additional participants may be enrolled to ensure adequate data at each dose level. The total number of participants to be enrolled will not exceed 204.

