5.5.3. Derived Endpoints

• SARS-CoV-2 RNA

Efficacy Endpoint of SARS-CoV-2 RNA will be converted to log₁₀ scale. Listings will include the values in log₁₀ scale and in the original scale. For SARS-CoV-2 RNA values reported as below the limit of detection/quantification (the lower limit of quantification is 1018 copies/mL), 1017 copies/mL will be used in the analyses.

SARS-COV-2 RNA below the limit of detection/quantification will be considered as undetectable (negative) in the analyses.

• SARS-CoV-2 RNA Rate of Decline

The individual rate of SARS-CoV-2 RNA decline will be derived as Average Area under the Curve minus Baseline (AAUCMB, i.e., the average daily viral load value minus baseline) for the five time intervals of: D1-D3, D1-D5, D1-D7, D1-D14 and D1-D28 using the following formulas:

AAUC =
$$\frac{\sum_{i=1}^{n-1} (t_{i+1} - t_i) (\frac{x_{i+1} + x_i}{2})}{(t_n - t_1)} = \frac{AUC}{(t_n - t_1)}$$
, and
AAUCMB=AAUC – Baseline (x at time i=1)

where, x_i is the data value at the ith time point and t_i is the time value at the ith time point.

• Time to non-detectable SARS-CoV-2 viral RNA in NP swabs based on PCR

Two consecutive undetectable viral RNAs in NP swabs (or one negative with no further followup) will be required to achieve the event. The date of the first undetectable result will be the event date. If the subject only has undetectable viral RNA at the last on study assessment, it will be counted as event at the time of the last assessment. Subjects not achieving the event and who complete the study follow-up will be censored at the last viral RNA assessment. Subjects not achieving the event and dropped out before Day 28 will be censored at Day 28.

Time to un-detectable = Date of Event (Censored) – date of first dose+1

• Time to negativity of infectious virus isolation in NP swabs based on infectious virus isolation determined by isolation in Vero cell line culture

This endpoint will be derived similarly to time to undetectable viral RNAs in NP swabs based on PCR. Infectious virus will be measured at Days 1, 3, 5, and 7 and additional details will be provided in the CSR.

• Time to COVID Symptom Resolution:

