9. EFFICACY ANALYSES

9.1. Efficacy Analyses

SARS-CoV-2 RNA

The actual and change from baseline in SARS-CoV-2 RNA (log 10) will be summarized by treatment and visit in tabular and graphic format using descriptive statistics for each specimen type. Individual SARS-CoV-2 RNA over time will be plotted by treatment.

Treatment comparisons between each active dose group and placebo group in SARS-CoV-2 RNA change from baseline will be analyzed using a mixed model for repeated measures (MMRM) with restricted maximum likelihood estimation and an unstructured covariance matrix. This model corrects for dropout and accounts for the fact that measurements taken on the same subject over time tend to be correlated, by using all available information on subjects within the same covariate set to come up with an estimate of the treatment effect for a dropout free population. The statistical model will be fitted with terms for treatment group, visit, treatment by visit interaction, baseline SARS-CoV-2 RNA and baseline SARS-CoV-2 RNA by Visit interaction. The estimated treatment difference for "Active – Placebo" at each visit will be displayed in the summary of statistical analysis together with the 95% confidence interval and the associated p-value. Least Squares Means for each visit will also be presented with the standard error. Least Squares Means and estimated treatment differences for each visit and the associated 95% confidence interval will be displayed graphically.

Sensitivity analyses will be conducted using an Analysis of Covariance (ANCOVA) model with terms for treatment group and baseline SARS-CoV-2 RNA by each study visit. The estimated treatment difference for "Active – Placebo" at each visit will be displayed in the summary of statistical analysis together with the 95% confidence interval and the associated p-value. Least Squares Means for each visit will also be presented with the standard error. If parametric assumptions are violated, non-parametric tests (e.g., extended Mantel-Haenszel test) may be utilized to provide a p-value for sensitivity analysis.

The number and percent of subjects with SARS-CoV-2 RNA of \leq LLOQ, or SARS-CoV-2 RNA reduction of \geq 1, 2, or 3 log₁₀ from baseline will be presented for each treatment group by visit. P-values for between-group comparison may be included as descriptive statistics using a 2 sample binomial test.

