Time to response un-detectable Viral RNA will be summarized using Kaplan-Meier method. The median time to response and the cumulative probability of response by visit along with the 95% confidence intervals will be provided by treatment group.

The baseline adjusted average area under curve (AAUCMB) through Day 3, Day 5, Day 7, Day 14 and Day 28 will be derived and summarized by treatment group. Between groups comparisons will be performed using an ANCOVA model with terms for treatment group and baseline SARS-CoV-2 RNA. The estimated treatment difference for "Active – Placebo" at each visit will be displayed in the summary of statistical analysis together with the 95% confidence

interval and the associated p-value. Least Squares Means for each visit will also be presented with the standard error.

The number and percent of subjects with negative infectious virus isolation based on qPCR assay will be summarized for each treatment group by visit. P-values for between-group comparison may be included as descriptive statistics using a 2 sample binomial test.

Time to negativity of infectious virus isolation will be summarized using Kaplan-Meier method. The median time to response and the cumulative probability of response by visit along with the 95% confidence intervals will be provided by treatment group.

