11. CHANGE FROM ANALYSIS PLANNED IN PROTOCOL

Due to lack of availability of subjects in the "early" time from symptom onset stratum, the between group comparison for the time to non-detectable SARS-CoV-2 viral RNA will be performed using an un-stratified log-rank test.

Statistical comparisons of safety endpoints between treatment groups in Part 1 will not be performed. All safety data will be presented descriptively.

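### The Part 1 primary test of time to undetectable RNA makes no use of Day 1 viral load; a baseline-adjusted comparison should be prespecified beside it, for precision and robustness to chance imbalance

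*SAP*

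**What the plan says.** SAP 2.3 makes time to undetectable RNA in Part 1 the only formally tested hypothesis. SAP 9.1 describes estimation for it: "Time to response un-detectable Viral RNA will be summarized using Kaplan-Meier method", with medians and cumulative probabilities by treatment group. The test is fixed in SAP 11, which drops the protocol's early/late symptom-onset strata and states that the comparison "will be performed using an un-stratified log-rank test". No covariate or other stratum replaces them.

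The event (SAP 5.5.3) is two consecutive undetectable results, or one with no further follow-up. "The date of the first undetectable result will be the event date". Undetectable means below a fixed level: "the lower limit of quantification is 1018 copies/mL".

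Elsewhere baseline RNA is used. The MMRM in SAP 9.1 includes "baseline SARS-CoV-2 RNA and baseline SARS-CoV-2 RNA by Visit interaction", and the by-visit ANCOVA and the AAUCMB ANCOVA also carry it as a term. SAP 5.3.6 allows baseline characteristics to be explored as covariates, but names neither baseline RNA nor this endpoint.

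**The concern.** Clearance is a crossing of a fixed floor. At the same rate of decline, a participant who starts higher crosses later, so Day 1 RNA should be prognostic by the construction of the endpoint. It is measured before the first dose, and the sponsor already treats it as worth adjusting for in the other modelled RNA comparisons. Part 1 randomization does not balance on it, and once the onset strata are dropped the primary test uses no prognostic information.

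With about 22 per arm, chance differences in starting viral load are not negligible. If the arms differ, the unadjusted test attributes part of that difference to the drug, or hides a real effect behind it. A prespecified adjusted comparison would show which reading is right. One chosen after unblinding would carry little weight.

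**Working it through.** **Inputs from the documents.** 44 enrolled, about 22 per arm, 1:1; 19 evaluable per arm after up to 10% missing (Protocol 10.5). Alpha is 0.10 and "all statistical tests will be two-sided" (Protocol 10.7.3). Swabs fall on Days 1, 3, 5, 7, 14 and 28. Placebo detection from the table under Protocol Figure 8 is 88/71/52/10/0% on Days 3/5/7/14/28. The active curve at a risk difference (RD) of -30% is 58/41/22/0/0%.

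**Assumptions.** The RD -35% curve is not tabulated; I take placebo minus 35 points, floored at zero. Baseline log10 RNA is standard normal and linked to clearance time by a Gaussian copula with correlation ρ. The documents do not give ρ, so I use 0 to 0.7.

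**1. The plan's own figure.** The SAP claims 88% power for a risk difference "of -35% for the primary endpoint using an alpha=0.10 type I error rate". Simulating the unadjusted log-rank test, Z = Σ(O−E)/√ΣV, on the real visit days gives 0.89-0.90 at 19 per arm, 0.91 at 20 and 0.92-0.93 at 22. The claim reproduces without any adjustment. (The Protocol attaches 88% to RD -30%. On the real visit days that gives 0.80 at 19 per arm and 0.84 at 22; it reaches 0.88 only if Days 2, 4 and 10 count as swab days. That is a separate point.)

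**2. Overall type I error.** With no drug effect, the unadjusted test rejects in 0.09-0.11 of trials for every ρ tried, against 0.10 nominal.

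**3. How often imbalance occurs.** The SD of the difference in baseline means is √(2/n) in SD units.
- 22 per arm: √(2/22) = 0.30; P(|difference| ≥ 0.5) = 2[1 − Φ(0.5/0.3015)] = 9.7%.
- 19 per arm: √(2/19) = 0.32; P = 12%.
- The Protocol lets Part 1 be called full at 24. At 12 per arm, √(2/12) = 0.41 and P = 2[1 − Φ(1.22)] = 22%.

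**4. With and without adjustment.** The adjusted test is a permutation-type score test on residuals from a Cox model on continuous baseline RNA. Two-sided 0.10, 22 per arm, unadjusted → adjusted:

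| ρ | Power, RD -35% | Power, RD -30% | False rejection given imbalance ≥ 0.5 SD in either direction | Power, RD -35%, drug arm ≥ 0.5 SD higher |
|---|---|---|---|---|
| 0 | 0.92 → 0.92 | 0.85 → 0.84 | 0.07-0.09 → 0.08-0.10 | 0.92 → 0.89 |
| 0.3 | 0.92 → 0.93 | 0.85 → 0.86 | 0.10-0.15 → 0.07-0.12 | 0.80 → 0.89 |
| 0.5 | 0.92 → 0.95 | 0.85 → 0.89 | 0.20-0.23 → 0.09-0.12 | 0.70 → 0.93 |
| 0.7 | 0.92 → 0.99 | 0.84 → 0.94 | 0.32-0.38 → 0.07-0.10 | 0.56 → 0.99 |

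At 19 per arm and RD -35%, power goes 0.89 → 0.88, 0.90 → 0.90, 0.89 → 0.92 and 0.89 → 0.97. The conditional columns rest on the roughly 10% of 4000 trials with such an imbalance (5% for the last column). Their simulation error is therefore about √(0.1×0.9/390) = 0.015 for the false-rejection column and √(0.7×0.3/200) = 0.03 for the last.

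**5. A cruder adjustment.** A log-rank test stratified at the median baseline gives 0.92, 0.93, 0.95 and 0.98 power (RD -35%, 22 per arm). At ρ = 0.7 its false rejection given imbalance is still up to 0.15-0.17 in these runs, so a two-way split can leave some of the imbalance uncorrected. Allowing for this version and for simulation error, I put the average gain at about 0-1, 2-4 and 4-11 points for ρ = 0.3, 0.5 and 0.7.

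**6. Is ρ in that range plausible?** Take clearance time as (baseline − 3.01)/slope, where 3.01 = log10(1018). With assumed baseline mean 5-7 log10, SD 1-1.5, and independent slopes with CV 0.3-0.8, the rank correlation is 0.34-0.89. This shows only that the range is not fanciful.

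**The case against.** The strongest reply is that nothing is broken. Randomization makes the unadjusted test valid, and a 10% chance of a 0.5 SD imbalance is variation that its p-value already allows for. That stands: a reader might infer an inflated type I error, but step 2 shows otherwise. The raised rates are conditional on an imbalance that has already happened.

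Nor is planned power lost, which is another tempting inference. The 88% was stated for a log-rank test with no covariate and is met. The shortfall exists only against a better test, and at ρ = 0.3 it is a point at most.

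The SAP also offers partial cover. Baseline RNA is summarized (SAP 7.3), so an imbalance would be seen. The adjusted MMRM and AAUCMB results give supportive evidence. SAP 5.3.6 permits exploratory covariates. Part 1 randomization was stratified by time since symptom onset, which Protocol 2.1 links to viral load. These points soften the concern without closing it. The supportive models answer a different question from time to clearance, and the covariate clause is discretionary. The onset strata balanced little if, as SAP 11 says, few early presenters were available.

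**Conclusion.** The point holds as a case for precision and robustness, not as an error in the planned test. The primary comparison leaves out a pre-dose measurement that the endpoint's definition makes likely to be prognostic and that the SAP uses in its other RNA models.

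The larger effect is conditional. In the roughly one trial in ten with a baseline difference of at least 0.5 SD, the unadjusted result can mislead in either direction, while the adjusted test stays near its nominal level. The average power gain is small at weak correlation and material only at strong correlation. All sizes depend on ρ, on the Gaussian link and on the Figure 8 curves; ρ is assumed. The documents do not support discarding the un-stratified log-rank test as invalid or underpowered for the SAP's stated effect.

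**What to change.** In SAP 9.1 and 11, prespecify for Part 1 a baseline-adjusted treatment comparison of time to undetectable RNA, reported alongside the un-stratified log-rank test. Use a Cox model, or a discrete-time complementary log-log model given the few visit days, with arm and continuous Day 1 log10 RNA. Add a permutation p-value if an exact test is wanted. Label its hazard ratio as conditional on baseline RNA, since it need not equal the unadjusted one.

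Add two rules:
- **Missing Day 1 RNA.** The SAP's mITT definition does not require a baseline value, and SAP 5.6 at most imputes a positive status, not a number. Keep these participants in, for example with a single blinded pooled-mean value plus an indicator. A separate missing stratum with one participant, or from one arm only, contributes nothing to a stratified log-rank test and so drops those participants.
- **Day 1 RNA already below the limit.** SAP 5.5.3 supplies a substitute value (1017 copies/mL) but does not say how such a participant enters the time-to-event analysis. State it, and apply the same rule to both analyses.

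Fix the wording before the planned unblinded analysis of Parts 1-6 (SAP 4.1), and have it written by staff who have not seen the unblinded virology data that section lets a sponsor group review.

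Cost: SAP text, one extra model, and about 1 point of power in the adjusted comparison if baseline RNA proves non-prognostic. No new data are needed.

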9.2. RNA Sequencing

Comparison of RNA dependent RNA polymerase gene sequences will be provided using Next Generation sequencing, amino acid mutations and nucleotide changes based on the detection of changes that occur at $\geq 1\%$ will be flagged by subject and visit.

Treatment emergent mutations are defined as mutations that are not present at baseline. The number and percent of subjects with treatment emergent mutation at each amino acid position will be summarized by treatment group. The data will be presented separately based on the detection of changes occurring at $\geq 1\%$, $\geq 3\%$ or $\geq 10\%$. The between treatment group comparisons will be performed using a 2 sample test based on the average number of treatment emergent mutations.

Treatment emergent nucleotide changes are defined as nucleotide changes that are not present at baseline. The number and percent of subjects with treatment emergent nucleotide change at each amino acid position will be summarized by treatment group. The data will be presented separately based on the detection of changes occurring at $\geq 1\%$, $\geq 3\%$ or $\geq 10\%$. The between treatment group comparisons will be performed using a 2 sample test based on the average number of treatment emergent nucleotide changes.

The results of mutation analysis of SARS-CoV-2 nucleotide sequences compared to the reference SAS-CoV-2 Virus will be summarized by treatment and study visit. The results of mutation analysis of the post baseline vs. the baseline SARS-CoV-2 nucleotide sequences will be summarized by treatment. The data will be presented separately based on the detection of changes occurring at $\geq 1\%$, $\geq 3\%$ or $\geq 10\%$.

9.3. Participant Symptom Diary

Patient diary will be listed and individual symptom scores will be summarized by treatment and visit. The worst severity of all individual symptoms will be summarized by treatment and visit.

The following time to response endpoints will be derived and summarized using KM method

- Time to COVID Symptom Resolution (Overall)
- Time to patient reported general physical health of 3 or 4 (Very Good or Excellent)

- Time to patient reported returned to the (Pre-COVID) health
- Time to resolution of upper respiratory tract symptoms
- Time to resolution of common symptoms (based on the 13 or 12 symptoms)
- Time to resolution of cough

If the data warrants, the resolution or duration of individual symptoms may also be derived and summarized.

9.4. Ordinal Scale Clinical Improvement

Ordinal Scale Clinical Improvement data will be listed and summarized as a continuous score by treatment and visit. If the data permits, the time to hospitalization/death will be derived and summarized using KM method.

9.5. COVID Related Medical Visit

The number and percent of subjects with a COVID medical visit will be presented for each treatment group.

The number and percent of subjects hospitalized during the study will also be summarized by treatment group.

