1.3. Secondary Objectives

- 1.3.1. To determine if EIDD-2801 reduces the time (days) to negativity of infectious virus isolation in NP swabs from SARS-CoV-2-infected adults. Infectious virus isolation is determined by isolation in Vero cell line culture.
- 1.3.2. To compare the incidence of grade 2 or higher AEs and drug-related AEs between treatment arms.
- 1.3.3. To determine if EIDD-2801 reduces the shedding of SARS-CoV-2 RNA in NP swabs compared to placebo as measured by median change in RNA at Treatment Days 3, 5, 7, 14, and 28 as determined by quantitative RT-PCR.
- 1.3.4. To determine if EIDD-2801 increases viral RNA mutation rate. RNA mutation rate is measured by Next Generation sequencing.
- 1.3.5. To determine if EIDD-2801 changes the severity and duration of self-reported symptoms of COVID-19.
- 1.3.6. To determine if EIDD-2801 treatment reduces the proportion of participants who are hospitalized for COVID-19 related illness by Day 28.
- 1.3.7. To characterize the PK of EIDD-2801/EIDD-1931 in patients with COVID-19 following administration of study regimen.

1.3.8. To determine the relationship between drug exposure and viral elimination dynamics including time to clearance.

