Participant Symptom Diary

Symptom diary data will be listed and individual symptom scores will be summarized by treatment and visit. The worst severity at each visit from the individual symptoms will also be summarized by treatment group.

The time to improvement (defined as symptoms becoming 0=absent or 1=mild; if baseline is mild, then improvement is defined as symptoms becoming absent) in all items and by individual item will be summarized using the Kaplan-Meier method and compared between randomization arms using a log-rank test. The median time to improvement and the cumulative probability of improvement over time with 95% confidence intervals will be provided by treatment group. Additional statistical models will be explored to assess the between group difference. Details will be provided in the SAP.

WHO 9-Point Ordinal Scale and COVID-19 Related Medical Visits

Ordinal Scale Clinical Improvement data will be listed and summarized by treatment. If data permit, the time to hospitalization/death will also be derived and summarized using the Kaplan-Meyer method.

The proportion of participants who require additional medical visits (including telemedicine visits and hospitalization) related to COVID-19 will be summarized by treatment group and compared between active drug versus placebo using a risk difference and corresponding 95% CI.

Safety

All safety data will be provided descriptively by dose group and scheduled time of assessment where appropriate. Adverse events will be coded using the Medical Dictionary for Regulatory Activities (MedDRA). An AE is considered treatment-emergent if it begins or worsens in severity after the first dose of randomized study drug. The number and percentage of subjects with treatment-emergent AEs will be tabulated by system organ class (SOC) and preferred term. Additional AE summaries will be provided by severity, drug related AEs, AEs leading to study drug discontinuation, and serious AEs.

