2.1.2. Secondary Objectives

- To compare the incidence of grade 2 or higher AEs and drug-related AEs between treatment arms
- To determine if EIDD-2801 reduces the time (days) to negativity of infectious virus isolation in NP swabs from SARS-CoV-2-infected adults
- To determine if EIDD-2801 reduces the shedding of SARS-CoV-2 RNA in NP swabs compared to placebo as measured by median change in RNA at Treatment Days 3, 5, 7, 14, and 28 as determined by quantitative RT-PCR
- To determine if EIDD-2801 increases viral RNA mutation rate. RNA mutation rate is measured by Next Generation sequencing
- To determine if EIDD-2801 changes the severity and duration of self-reported symptoms of COVID-19

- To determine if EIDD-2801 treatment reduces the proportion of individuals that are hospitalized for COVID-19 related illness by Day 28
- To characterize the pharmacokinetics (PK) of EIDD-2801 in patients with COVID-19 following administration of study regimen
- To determine the relationship between drug exposure and viral elimination dynamics including time to clearance

2.1.3. **Exploratory Objectives**

- To determine if EIDD-2801 will prevent the composite endpoint of hospitalization, oxygen desaturation, oxygen requirement, mechanical ventilation, or death by 28 days after study entry
- To determine the comparability between site-collected NP and available OP swabs and available self-collected nasal mid-turbinate swabs for the quantification of SARS-CoV-2 RNA or quantitative culture
- To determine comparability between viral RNA detection and virus isolation from sitecollected NP swabs

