This endpoint will be derived similarly to the time to symptom resolution.

• Time to patient reported returned to the (Pre-COVID) health

This endpoint will be derived similarly to the time to symptom resolution.

• Time to resolution of upper respiratory tract symptoms (based on the worst severity of the 5 symptoms measured: Cough, Shortness of breath, Sore throat, Nasal obstruction and Nasal discharge)

This endpoint will be derived similarly to the time to symptom resolution.

• Time to resolution of common COVID symptoms (based on the worst severity of the 13 symptoms measured: Cough, Shortness of breath, Feeling feverish, Muscle aches, Diarrhea, Vomiting, Nausea, Headache, Sore throat, Nasal obstruction, Nasal discharge, Fatigue and Chills)

This endpoint will be derived similarly to the time to symptom resolution.

• Time to resolution of common COVID symptoms (based on the worst severity of the 12 symptoms measured: Cough, Shortness of breath, Feeling feverish, Muscle aches, Diarrhea, Vomiting, Nausea, Headache, Sore throat, Nasal obstruction, Nasal discharge and Chills)

This endpoint will be derived similarly to the time to symptom resolution.

• Time to resolution of Cough

This endpoint will be derived similarly to the time to symptom resolution.

• COVID related medical visit

A subject is considered to have a COVID related medical visit if the subject meets any of the following:

- 1. Hospitalized based on the Hospitalization CRF or any outpatient medical visit (including telemedicine visits)
- 2. Answered "Yes" to the Diary question 'Sought urgent medical care at an emergency room or clinic'
- 3. Answered "Yes" to the Diary question "Been hospitalized for at least 24 consecutive hours"

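### SAP 9.5 replaces the protocol's risk difference and 95% CI for COVID-19 medical visits with bare counts, without listing the change, and SAP 5.5.3 calls any visit COVID-related

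*SAP*

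**What the plan says.** **Objective.** Protocol 1.3 lists as a secondary objective: "To determine if EIDD-2801 treatment reduces the proportion of participants who are hospitalized for COVID-19 related illness by Day 28". SAP 2.1.2 repeats it almost word for word: "To determine if EIDD-2801 treatment reduces the proportion of individuals that are hospitalized for COVID-19 related illness by Day 28". The objective is comparative, specific to COVID-19, and tied to Day 28.

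**Protocol analysis.** Under clinical outcomes, Protocol 10.8 takes "The proportion of participants who require additional medical visits (including telemedicine visits and hospitalization) related to COVID-19" and says it will be "compared between active drug versus placebo using a risk difference and corresponding 95% CI". The same section rules out formal tests for the pooled analyses but promises estimated between-group differences with 95% confidence intervals.

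**SAP analysis.** SAP 9.5 has two sentences: "The number and percent of subjects with a COVID medical visit will be presented for each treatment group" and "The number and percent of subjects hospitalized during the study will also be summarized by treatment group". Neither gives a difference or an interval. SAP 9.4 adds a conditional summary: "If the data permits, the time to hospitalization/death will be derived and summarized using KM method". SAP 9.6 gives number and percent for an exploratory composite that includes hospitalization.

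**Derivation.** SAP 5.5.3 counts a subject as having a COVID-related medical visit if any of three criteria is met. The first reads "Hospitalized based on the Hospitalization CRF or any outpatient medical visit (including telemedicine visits"). The other two are diary answers, on urgent care and on hospitalization for at least 24 hours. None, as the SAP words them, asks for the cause.

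**Precedence.** SAP 1 says the SAP supersedes the protocol's statistical section and that substantial differences will be identified. Protocol 10.7 and 10.8 also let the SAP prevail. SAP 11 lists two changes: an un-stratified log-rank test for time to non-detectable viral RNA, and no statistical comparison of safety endpoints in Part 1.

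**The concern.** A comparison planned in the protocol is absent from the document that governs the analysis, and the section meant to record such changes does not mention it. Separately, the label and the rule disagree: the SAP heading says COVID-related, but the derivation does not require any link to COVID-19.

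Hospitalizations may be few in this outpatient trial. Two bare percentages then invite over-reading in either direction: a reader may see a halved rate, or no effect, in data that can hardly separate the two. An interval fixed in advance prevents that, and one computed later would use a method chosen after the data were seen. Unattributed events add a second problem. Hospital stays or clinic visits unrelated to COVID-19 fall on both groups and pull the ratio of risks towards 1.

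**Working it through.** The point rests on text. The plan states no sample size, power or event rate for this outcome, so there is no figure of the plan's to reproduce.

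**1. Analyses side by side**

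| Outcome | Protocol | SAP |
|---|---|---|
| COVID-19 medical-visit composite, pooled | Risk difference, 95% CI (10.8) | n and % (9.5) |
| Hospitalization alone, as a proportion | None specified | n and % (9.5) |
| Time to hospitalization or death, pooled | KM summary if data permit (10.8) | KM summary if data permit (9.4) |
| Death or hospitalization, Part 1 | KM and 28-day risk, set out with the safety analyses (10.7.3.1, 10.7.3.2) | Part 1 safety comparisons removed (11) |

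The first row is the loss that SAP 11 does not list. The SAP handles this outcome in Section 9, Efficacy Analyses, and the protocol's comparison belongs to the pooled analyses. The SAP 11 statement on Part 1 safety endpoints therefore does not cover it.

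**2. Size of the missing interval**

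The group totals come from the sample treatment assignment table in Protocol 3: active 22 + 8 × 12 = 118, placebo 22 + 8 × 4 = 54. Event counts are assumed. The method is Newcombe's hybrid score interval. For each group with x events among n, the Wilson limits are

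(x + z²/2 ± z√[n p(1 − p) + z²/4]) / (n + z²), with p = x/n and z = 1.96.

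For d = p1 − p2 (active minus placebo), the limits are

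lower = d − √[(p1 − l1)² + (u2 − p2)²]; upper = d + √[(u1 − p1)² + (p2 − l2)²].

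Worked case, 2/118 and 2/54:

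- Active: p1 = 1.69%, Wilson 0.47% to 5.97%.
- Placebo: p2 = 3.70%, Wilson 1.02% to 12.54%.
- d = 1.69 − 3.70 = −2.01 points.
- Lower: −2.01 − √(1.22² + 8.84²) = −2.01 − 8.92 = −10.93.
- Upper: −2.01 + √(4.28² + 2.68²) = −2.01 + 5.05 = +3.04.

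Other assumed counts, by the same formula:

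| Active | Placebo | Difference (points) | 95% CI |
|---|---|---|---|
| 0/118 | 0/54 | 0.0 | −6.6 to +3.2 |
| 1/118 | 3/54 | −4.7 | −14.3 to +0.6 |
| 3/118 | 3/54 | −3.0 | −12.7 to +2.9 |
| 6/118 | 5/54 | −4.2 | −15.2 to +3.5 |
| 12/118 | 11/54 | −10.2 | −23.4 to +0.7 |
| 18/118 | 16/54 | −14.4 | −28.6 to −1.4 |

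The upper rows illustrate rare events such as hospitalization. The last two illustrate a commoner event, as the medical-visit composite might be.

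**3. Effect of unattributed events**

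Assume true COVID-19 risks of 5% (placebo) and 2.5% (active), a risk ratio of 0.50, and an unrelated risk c that is equal in both groups. The observed risk is p + c − pc.

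- c = 1%: 3.475% / 5.95% = 0.58.
- c = 2%: 4.45% / 6.90% = 0.64.
- c = 5%: 7.375% / 9.75% = 0.76.

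The risk difference moves only from −2.5 to −2.4 points. Missing attribution therefore distorts a comparison of the two percentages as a ratio much more than it distorts the difference.

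**The case against.** The strongest reply is that little is lost. The trial is a virology proof of principle, the pooled analyses carry no formal tests, and this outcome was never sized. Counts and denominators by group remain, so a reader can compute an interval. SAP 1 promises to identify only substantial differences, and omitting a descriptive interval may not qualify. All of this bears on severity, and it is right that no primary or virology result is affected. It does not explain the omission: Protocol 10.8 promises the estimate and its interval even though no test is planned, and an interval that readers construct themselves is not prespecified.

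Three stronger readings are tempting and should be set aside.

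- **That the SAP dropped a protocol risk difference for hospitalization itself.** The protocol has none; its risk difference is for the composite. A separate hospitalization row is an addition that serves the stated objective.
- **That the SAP chose to count hospitalization from any cause.** It does not say so, and the sentence sits under a COVID-related heading. The reading comes from the absence of attribution in 9.5 and 5.5.3. The protocol's own Part 1 analyses of death or hospitalization do not restrict hospitalization to COVID-19 either.
- **That the Part 1 hospitalization comparison vanished unannounced.** It is set out with the safety analyses, so the SAP 11 statement on Part 1 safety comparisons arguably discloses its removal.

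**Conclusion.** The concern holds for one undisclosed change and one derivation gap. The prevailing SAP replaces the protocol's risk difference and 95% CI for the COVID-19 medical-visit composite with number and percent, and SAP 11 does not list this. SAP 5.5.3 and 9.5 require no link to COVID-19, although the objective does.

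It would go too far to infer that the objective is left with nothing. The SAP still reports hospitalization by group, a conditional Kaplan-Meier summary, and a 28-day exploratory composite. Follow-up ends at Day 28, so a count over the study is in effect a Day 28 count. What is missing is a prespecified between-group estimate with its precision.

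The size can only be illustrated, because every event count above is assumed. At 118 versus 54, intervals for rare events span roughly 10 to 19 points, and most of the illustrated intervals include zero. The restored interval would mainly show how little the hospitalization data can exclude. Whether existing records allow attribution to COVID-19 cannot be judged from these documents, because the CRF is not shown.

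**What to change.** 1. In SAP 9.5, restore the active (pooled and by dose) minus placebo risk difference for the COVID-19 medical-visit composite, with a named small-sample 95% CI such as Newcombe's score interval. State that it is descriptive estimation without a formal test.
2. Add the same estimate for COVID-19 related hospitalization of at least 24 hours by Day 28, identified as a new row for the secondary objective. Keep all-cause hospitalization as a second row.
3. In SAP 5.5.3, count a CRF hospitalization or an outpatient visit only if it is recorded as COVID-19 related, where existing records allow this. Say how the two diary answers are handled.
4. List in SAP 11 any departure from Protocol 10.8 that is kept.

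The cost is SAP wording, one added column and one or two rows in an existing table, and a change to one derivation. No new data collection is proposed. If cause cannot be recovered from the records, the SAP should say so and label the counts as all-cause.
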